6.2 Randomized Intervention Study

General study design and justification of design

This is a pragmatic cluster randomized controlled clinical trial investigating a new algorithm combining PCT measurement and lung ultrasonography results for the management of LRTIs among adults in GPs practices. Every consecutive patient meeting the inclusion criteria will be included in the study. All patients will be evaluated by the GP at the time of enrolment (day 0) and will have follow-up evaluations on day 7 and 28 via a phone interview by the study team to ask for the presence of LRTI symptoms, of side effects from antibiotics, secondary antibiotic use, number of follow-up visits, secondary hospitalization or death (Figure 2). In case of clinical deterioration, the patient will have a follow-up evaluation at any time, if possible with the same GP. We plan to enrol patients for a period of 15 months to reach the estimated sample size.

Methods of minimising bias

The study will be randomized. To avoid contamination between arms, randomization will be performed at GP level and only one GP per practice will be included. The cluster effect related to GP was taken into account while calculating the sample size and the outcome measures.

Details concerning GPs recruited in the study will be entered in a database using REDCap[©]. The randomization module of the REDCap software will then be used to attributed each of the GPs to one of the three study arms. We will perform a simple randomization using a 1:1:1 ratio.

[figure not shown]

Figure 2: Study design of the randomized intervention study

Study Setting

This study will be carried out in GPs practices located in different Swiss regions to ensure a representation of different cultural areas (German-speaking part (Bern) and French-speaking part of Switzerland (Vaud, Neuchâtel, Fribourg, Valais and Jura)). Each participating GP will be responsible to enrol consecutive eligible patients (total of 15 patients) in the study

These regions have been chosen because of good collaboration with a strong network of GPs during previous studies which assures the feasibility of the study [8, 9]. These regions have also been chosen to assure representativeness regarding differences in antibiotic prescription practices [37]

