In case of elevated PCT result ($\geq 0.25 \mu\text{g/L}$), a lung ultrasound will be performed to look for the presence of a lung infiltrate or consolidation suggesting the presence of CAP (Figure 3). Lung ultrasonography using the Phillips© Lumify portable ultrasound with a L12-4 (convex) transducer will be performed. The ultrasound will be provided to the GPs by the study team.

The lung ultrasound will be done following international evidence-based recommendations for point-of-care lung ultrasound using a ten points sonographic technique and the criteria for positive scan and positive examination for the diagnosis of pneumonia [39, 40]. The lung ultrasound is expected to last for 15 minutes.

Antibiotics will be prescribed only if a lung infiltrate or consolidation is identified during lung US. The choice, dosage and duration of antibiotic treatment will be left to the discretion of the GP.

Naso-pharyngeal swabs and venous blood samples will be systematically collected for further exploratory analysis. Sputum will also be collected if the patient is able to produce it.

Arm 2: PCT

GPs randomly assigned to the PCT arm will be responsible to recruit patients fulfilling the inclusion criteria and manage them using the PCT result.

GPs in this group will also receive training detailed training (described in section 8.2.1) on the epidemiology and management of pneumonia in Switzerland as part of the intervention.

The PCT point-of-care test will be performed, as described above, to decide on antibiotic prescription. Antibiotics will be prescribed only in case of elevated PCT ($\geq 0.25 \mu\text{g/L}$) (Figure 3). The choice, dosage and duration of antibiotic treatment will be left to the discretion of the GP.

Naso-pharyngeal swabs and venous blood samples will be systematically collected for further exploratory analysis. Sputum will also be collected if the patient is able to expectorate.

Control Intervention (standard/routine/comparator treatment / medical device)

Arm 3: usual care arm

GPs randomly assigned to the usual care arm will be responsible to recruit patients fulfilling the inclusion criteria and will manage and treat these patients as they usually do (Figure 3). They will not receive any additional training.

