8.3 Intervention modifications

The GPs may modify the allocated intervention or administer components of the intervention at time points not specified beforehand.

The proportion of modification of the intervention in each intervention arm will be recorded. The adherence to the treatment recommendations resulting from pre-defined patient management will be recorded. Data will be used for the intention to treat analysis.

Such findings will inform us on the feasibility and scalability of the study on a larger scale.

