11.2 Determination of Sample Size

The sample size was calculated to assess a decrease in antibiotic prescription of at least 15% between the UltraPro and the PCT arms as well as 15% between the PCT arm and usual care.

The proportion of patients receiving antibiotics with the usual care is estimated to be around 60% and to decrease to 45% using PCT and to 30% combining PCT and ultrasound. These numbers have been extrapolated from the subgroup of patients with LRTI in a study at primary care level in the Netherlands [3].

A study sample of 14 GPs and 15 patients per GP in each arm (210 patients per arm and a total of 630 patients) gives a power of 80% to detect a decrease in antibiotic prescription from 60% (usual care) to 45% (PCT), and from 45% (PCT) to 30% (UltraPro), with 5% level of significance, when adjusting for clustering at practice level (intracluster coefficient 0.06) [3]. This sample size guarantees a power of 80% to prove non-inferiority in terms of duration of activities restriction (non-inferiority margin=1 day, standard deviation=4 days) as well as of composite adverse outcome (probability in the “usual care” arm 0.05 with a non-inferiority margin of 0.02). Simulations used to determine the sample size are shown in the following figures.

[figure not shown]

Figure 4: Statistical simulations used to determine sample size

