11.4 Planned Analyses

Datasets to be analysed, analysis populations

The analysis will be performed in intention to treat (pragmatic trial). The analysis population will comprise all patients included by the randomised GPs. The primary analysis will include all patients enrolled in the study, irrespective of follow-up. Patients who are lost to follow-up will be considered as having had a clinical failure, an adverse outcome and duration of disease equal to the maximum duration measured in the other patients. Patients in whom GPs did not follow the respective algorithm recommendation and/or who did not have complete telephone follow-up will be excluded from the per-protocol analysis.

Primary Analysis

Odds ratio of antibiotic prescription between 2 groups as well as the difference in proportion of patients prescribed an antibiotic by day 28 using logistic regression corrected for variation at the GP level (generalized linear mixed effect)

Secondary Analyses

The following statistical analyses are planned:

- Difference between the mean number of days with restricted activities by day 14 using linear mixed effect regression
- Difference between the mean number of medical consultations by day 28 using linear mixed effect regression
- Odds ratio of adverse outcome between 2 groups as well as the difference in proportion of patients with adverse outcome and clinical failure using logistic regression corrected for variation at the GP level (generalized linear mixed effect)
- Difference between the mean daily symptom scores measured in the different arms. The effects of the interventions on recovery will be studied by comparing the slopes of symptom scores over time between arms
- Difference in the mean duration of total time spent in the practice using linear mixed effect regression
- Difference in levels of satisfaction of providers and of patients between arms
- Difference in the mean cost per arm using linear mixed effect regression
- Diagnostic performance of:
 - individual host biomarker(s) based on crude positive and negative likelihood ratios, and on the area under the curve of receiver operator characteristic (ROC) curves, to predict the development of a life-threatening disease, clinical failure, or the presence of pneumonia (using a clinical diagnosis).

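### Simple 1:1:1 randomization of 42 GPs does not secure the 14 GPs per arm that the sample size assumes; the average cost is about 2 power points per contrast, and a restricted list would avoid it

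*Combined protocol and SAP*

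**What the plan says.** Section 6.2 (Methods of minimising bias) randomizes at GP level, with one GP per practice, through the REDCap randomization module: "We will perform a simple randomization using a 1:1:1 ratio". It names no blocks, strata, minimisation or other device that would fix the arm sizes.

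Section 11.2 rests the power statement on "A study sample of 14 GPs and 15 patients per GP in each arm". The synopsis gives the same totals: 42 GPs, 15 patients each, 210 patients per arm.

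Section 7.2 provides for replacing a GP only when the GP leaves before the training and randomisation session. The primary model in section 11.4 is "logistic regression corrected for variation at the GP level (generalized linear mixed effect", fitted between two groups at a time.

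On regions, section 6.2 states: "These regions have also been chosen to assure representativeness regarding differences in antibiotic prescription practices". Region is neither a stratum nor a model term.

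**The concern.** The allocation method and the sample-size premise do not match. In unrestricted simple randomization each GP is drawn independently, so the numbers per arm are random. With 42 units and three arms they can differ noticeably from 14.

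Each pairwise contrast rests on about 28 GPs. The GP is the unit of randomization and patients are clustered within GPs, so losing a few GPs from one arm widens the standard error of every contrast that uses it. What is at stake is precision. The trial makes only one draw, so the spread of outcomes matters as well as the average.

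**Working it through.** **Inputs.** 42 GPs, 14 per arm, m = 15 patients per GP, ICC 0.06, 60% v 45% and 45% v 30%, 5% significance (section 11.2). Two-sided testing is an assumption, because the plan does not state sidedness.

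**The plan's own figure (80%).** The design effect is 1 + (15 − 1) × 0.06 = 1.84, so the effective n per arm is 210/1.84 = 114.1. Power = Φ(|p1 − p2|/SE − 1.96), with SE² = p1(1 − p1)/n1 + p2(1 − p2)/n2.

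- 60 v 45: SE = √[(0.24 + 0.2475)/114.1] = 0.0654; 0.15/0.0654 = 2.295; Φ(0.335) = 63.1%.
- 45 v 30: SE = √[(0.2475 + 0.21)/114.1] = 0.0633; 0.15/0.0633 = 2.369; Φ(0.409) = 65.9%.

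The stated 80% is therefore not reproduced. With a pooled variance under the null the figures are 62.3% and 65.0%. On that version, 80% for both contrasts needs an ICC of about 0.015 (80.0% and 82.5%). The simulation figure in section 11.2 is not shown, so the plan's exact method cannot be checked. Allocation does not cause this gap, because the calculation already assumes 14 per arm.

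**Arm sizes under simple allocation.** The counts follow Multinomial(42; 1/3, 1/3, 1/3).

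- P(14/14/14) = 42!/[(14!)³ × 3⁴²] = 1.9%.
- P(some arm ≤ 10) = 36.6%; P(some arm ≤ 8) = 9.5%; expected smallest arm 10.9 GPs.

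**One example, 10 v 14 GPs, 60 v 45.** The effective sizes are 150/1.84 = 81.5 and 114.1. SE = √(0.24/81.5 + 0.2475/114.1) = 0.0715; 0.15/0.0715 = 2.098; Φ(0.138) = 55.5%, against 63.1% for 14 v 14.

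**Power over all splits, weighted by their probability (ICC 0.06).**

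| Contrast | Fixed 14 v 14 | Mean, simple | Mean loss | P(loss ≥ 5 points) | 5th percentile |
|---|---|---|---|---|---|
| 60 v 45 | 63.1% | 61.3% | 1.8 | 25% | 51.5% |
| 45 v 30 | 65.9% | 64.0% | 1.9 | 26% | 54.2% |

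The means include draws in which a contrast gains because the third arm is short. With the pooled version the mean loss is 1.7 to 2.0 points for any ICC from 0 to 0.06. At an ICC of about 0.015 it is 80.0% to 78.1% and 82.5% to 80.6%. The size of the point therefore does not depend on which baseline power is right.

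**Validity.** Simulated type I error was 5.3% with fixed arms and 4.8% with simple allocation.

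**If some GPs are already allocated (ICC 0.06, pooled version), mean loss still left, in points:**

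| Already allocated | 1:1:1 blocks for the rest | Rest fills arms to 14 |
|---|---|---|
| 0 | 0.0 | 0.0 |
| 12 | 0.5 | 0.0 |
| 21 | 0.9 | 0.0 |
| 30 | 1.3 | 0.0 |
| 36 | 1.5–1.6 | 0.2 |
| 42 | 1.8–1.9 | 1.8–1.9 |

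**Predictability of a 14/14/14 list.** Take an observer who sees every earlier assignment and knows the totals. The number of assignments that are certain is 3 × 14/(28 + 1) = 1.45 of 42, or 3.4%. Always guessing the arm with most slots left is right with probability (largest remaining count)/(total remaining) at each step. Averaged over all orders from 14/14/14, this gives 18.5 of 42, or 44%, against 33% under simple allocation.

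**The case against.** Simple randomization is a valid method, and about 2 points of average power is small. Both statements stand, and they are why this is only an optional improvement. The average understates the risk of one bad draw, however, since a contrast loses 5 points or more about a quarter of the time.

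The word simple may have been meant loosely, as unstratified allocation from a balanced list. The fixed 14 per arm in section 11.2 makes that possible. The loss would then be zero and a clarification would be enough. As written, the term means unrestricted.

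The change may also come too late. The synopsis runs the study from September 2017 with a 5-month pilot, so the trial phase starts about February 2018, while version 5.0 is dated 7 May 2018. The documents do not say how many GPs had been allocated by then, so the recoverable part is unknown.

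A reader might infer that region must be a stratum and a model term. The documents do not support that. They mention differences in prescribing between regions but size no gap, give no number of GPs per region, and do not say that Bern differs from the French-speaking cantons. In the PCT arm, "Antibiotics will be prescribed only in case of elevated PCT", and the UltraPro arm has a similar rule based on ultrasound. Local habit should therefore act mainly in usual care, although "The GPs may modify the allocated intervention or administer components of the intervention at time points not specified beforehand". The gain computed here comes from balanced arm sizes and needs no stratum.

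**Conclusion.** The point holds as a minor, avoidable loss of efficiency. Simple allocation, read as unrestricted, leaves the 14 GPs per arm to chance. It costs about 2 power points per contrast on average, with about a 25% chance of losing 5 points or more on a given contrast. This rests on exactly 42 GPs with 15 patients each, a two-sided 5% test, a normal approximation and an ICC between 0 and 0.06 (the 25% on an ICC of 0.06).

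Two stronger readings are tempting and should be resisted. Chance imbalance in the number of GPs does not bias the comparison or inflate the type I error. Nor does it explain why the stated 80% is not reproduced at ICC 0.06: that discrepancy is separate and much larger, and balanced arms would still give only 63.1% and 65.9%.

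**What to change.** In section 6.2, replace simple randomization with a restricted, unstratified allocation list in the same REDCap module that fixes 14 GPs per arm. A randomly ordered list of 42 with 14 slots per arm would do, as would permuted blocks of varying, concealed size.

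- If some GPs are already allocated, put the slots needed to bring each arm to 14 in random order and use them for the remaining GPs.
- If all 42 are allocated, change nothing.
- If a balanced unstratified list was always intended, say so in one sentence.

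Stratification by language area and a region term are optional. If a region term is wanted, prespecify it before outcomes by arm are seen.

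**Cost.** A different list, with no new data or staff. The main downside is that later assignments become somewhat predictable, which matters because the synopsis directs invitations partly to GPs known to the investigators. Concealing the list from those who invite GPs, and entering all GPs of a training and randomisation session before any is allocated, limits this.

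**What it does not do.** It does not restore 80% power. It also does not prevent later loss of UltraPro GPs who are excluded after failing the second training test (section 8.2, Table 1).

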7. STUDY POPULATION

7.1 Pilot Study

Four ultrasound-naïve GPs at the *Permanence PMU-Flon* of Lausanne will undergo the ultrasound training curriculum. It is expected that they will perform lung ultrasound in at least 3 patients with LRTI per month during three to five months at the *Permanence* or at their private practice.

Eligible patients, as described below, will be recruited as per the protocol of the randomized intervention study.

7.2 Randomized Intervention Study

All patients presenting to a participating GP's office for a consultation for a LRTI will be screened for inclusion in the study.

Patients fulfilling all of the following inclusion criteria are eligible for the study:

- Informed consent as documented by signature
- Patients aged 18 years or more
- Acute cough (< 21 days) and at least one of the following symptom or sign:
 - o History of fever for more than 4 days
 - o Dyspnoea
 - o Tachypnoea (≥ 22 cycles per minutes)
 - o Abnormal focal finding during lung auscultation

The presence of any one of the following exclusion criteria will lead to exclusion of the participant:

- Previous prescription of antibiotics for the current episode
- Working diagnosis of acute sinusitis or of a non-infective disorder
- Cystic fibrosis
- Previous episode of COPD exacerbation treated with antibiotics during the last 6 months
- Known pregnancy
- Severe immunodeficiency (untreated HIV infection with CD4 count < 200 cells/mm³, solid organ transplant receiver, neutropenia, treatment with corticosteroids (dose equivalent to 20mg prednisone/day for > 28 days))
- Admission of the patient
- GP not available for performing study
- Patient unable to provide informed consent

Recruitment and screening

Every participating GP will be responsible to recruit consecutive eligible patients. All patients who in the GP's opinion have an ARI with cough, will be screened for eligibility. GPs will be responsible to check all inclusion and exclusion criteria. Sufficient time (10-15 minutes) to read the informed consent form and make an informed decision will be given to the patients before recruitment in the study. After this time the GPs will obtain written informed consent from the participants. If additional time is needed to make an informed decision the GP will decide whether or not he is available to allow more time for the patient to make the decision. If no additional time can be granted due to the pressures of the consultation flow of the GP's practice, the patient will be excluded from the study.

For all screened patients, antibiotic prescription will be recorded.

Criteria for withdrawal / discontinuation of participants

An individual patient may discontinue his participation in the study at any point in time, by informing his physician or the study team. In this case, the study team can use the data recorded up to the date that the patient informs of his wish to discontinue the study.

An individual patient may also choose to refuse the phone interview, without discontinuing the study itself. In this case, the investigators can access the medical file until the end of the 28 days observation period.

There are no foreseeable reasons for investigators to withdraw a patient from the study. Patients who are not reachable during follow-up will not have outcome data. They will be excluded from the analysis of the safety of the intervention but they will still be included in the assessment of impact on antibiotic treatment and of the feasibility of the intervention.

Physicians may choose to discontinue participating in the study. If so, they are responsible of informing the study team. If discontinuation occurs before the training and randomisation session, they will be replaced by another willing physician. If discontinuation occurs after patient recruitment, training and randomisation, patient outcomes will be collected by the study staff until the end of planned follow-up. Access to the medical files will be discussed on a case by case basis with the physician.

There is no foreseeable reason for the investigators to withdraw a physician from the study once he participated in patient recruitment, training and randomisation.

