3.4 Risks/Benefits

The risk of the therapeutic intervention is judged comparable in comparison to standard of medical care. The proposed investigations and management strategies are all part of routine optimal care. The risks of this study are minimal.

The risk related to venous puncture for blood drawing (17.5 ml) and naso-pharyngeal swab will be minimized by strict adherence to standard operational procedures and national guidelines.

A potential risk is related to the inappropriate withdrawal of antibiotic treatment in patients with CAP. There are numerous layers of safety included in the study design whose purpose is to diminish this risk:

- Patients with severe symptoms and requiring hospitalisation are excluded from the study, these will be managed as usual.
- Patients with severe COPD (defined for practical purposes as having had an exacerbation treated by antibiotics in the last 6 months) or severe immunodeficiency will be excluded from the study.
- In case of worsening symptoms, patients will be advised to consult their GPs or an emergency care centre. If antibiotic treatment is then warranted it will be administered. This is considered a delayed antibiotic prescription. A recent study, in 28'883 primary care patients, has not shown adverse outcomes associated with delayed antibiotic prescription for LRTIs [36].
- Procalcitonin-only guided prescription in patients with LRTIs has been previously shown to be safe in patients consulting emergency departments with severe LRTIs [23] and in a primary care setting [3, 24].

Patients will benefit from full history taking and physical examination. Diminished prescription of unnecessary antibiotic treatments is expected with an associated diminution in side effects, costs and resistances.

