5.2 Randomized Intervention Study

Primary outcome

Proportion of patients prescribed an antibiotic in each arm by day 28.

The following information will be collected to assess the proportion of patients prescribed an antibiotic in each arm by day 28:

- Day of the antibiotic prescription
- Antibiotic substance prescribed
- Dosage of antibiotic prescribed
- Duration of the antibiotic treatment prescribed

Secondary Outcomes

Clinical outcomes

- a. Duration of the episode: number of days during which the patient was symptomatic (defined by the daily symptom diary and telephone follow-up) within 28 days of follow-up.
- b. Duration of restricted daily activities: number of days during which the patient's daily activities (work or recreation) were restricted due to a respiratory tract infection.
- c. Clinical failure by day 7:
 - i. Admission to hospital within 7 days of follow-up
 - ii. Death within 7 days of follow-up
 - iii. No amelioration or worsening of relevant symptoms (fever and/or dyspnoea) at day 7
- d. Number of medical visits for the episode of LRTI within 28 days of enrolment.
- e. Serious adverse outcome: measured by day 28, based on the advent of at least one of the following events:
 - i. Death
 - ii. Secondary admission to hospital for any reason
 - iii. Complications (persistence of pneumonia, lung abscess, lung effusion, empyema or sepsis)
- f. Number of days with side effects related to antibiotics within 28 days of follow-up

The following information will be collected during telephone follow-up and recorded in the eCRF. It will also be obtained from the patient's diary.

Consultation process

- a. Median duration of time spent for the medical consultation, blood sampling, PCT measurement, lung US and total time spent in the practice.
- b. Quality of the ultrasound images. Agreement between GPs and experts on ultrasound images interpretation.
- c. Evaluation of the satisfaction of providers and of patients.

Economic aspects

- a. Cost / effectiveness ratio expressed as amount of money required per 1% absolute decrease of the proportion of antibiotic prescription.

Exploratory Outcomes

- a. Prevalence of different respiratory pathogens assessed by multiplex rt-PCR on nasopharyngeal swab and sputum
- b. Sensitivity and specificity of combinations of host biomarkers and gene expression signatures in identifying patients with serious adverse outcome, clinical failure or with pneumonia

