PaxGene	2.5 ml	-80°C	Transcriptomics

Table 2. Details of blood samples collected in the study

Naso-pharyngeal swabs

For future analyses, a naso-pharyngeal swab will be performed on all patients recruited in the study. A eSwab™ (Copan Diagnostics[©]) will be introduced in the nasal cavity until the naso-pharynx in one

nostrils. Swabbing will then be performed. The sample will then be conserved at -80°C using a liquid collection and transportation system.

A respiratory pathogen multiplex real time polymerase chain reaction (PCR) assay will be retrospectively performed in the laboratory of virology of Geneva University Hospital to identify the aetiological agent of the LRTI. Such an approach has been described in other studies [41].

Sputa

For future analyses, a sputum sample will be collected for all patients recruited in the study if they are able to produce it. The sample will then be conserved at -80°C.

A respiratory pathogen multiplex real time PCR assay will be retrospectively performed in the laboratory of virology of Geneva University Hospital and culture will be performed in the microbiology laboratory of Lausanne University Hospital to identify the aetiological agent of the LRTI.

Follow-up after initial assessment

Active surveillance

All participants will be contacted by phone at day 7 and day 28 by the study team.

At days 7 and 28, a standardized interview will be done to ensure that the patient is alive, to:

- evaluate clinical outcome (presence or recurrence of LRTIs symptoms)
- record any additional visits
- record additional antibiotic prescription
- record number of days during which daily activities (work or recreation) were restricted
- evaluate antibiotic side effects
- record secondary hospital admission
- patient satisfaction will be recorded at day 28 only

The caller will be blinded as to the arm in which the patient was included.

All participants will be asked to fill a daily diary until symptom resolution up to day 28. The diary can be filled in paper and returned by post or for participants who prefer an electronic version will be made available.

They will report each day on 6 items:

- coughing
- phlegm
- shortness of breath
- sleep disturbance
- impairment of normal daily activities
- generally feeling unwell

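### Unreachable patients stay in the primary day-28 antibiotic analysis, but the plan has no systematic source and no missing-data rule for their prescriptions after day 0

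*Combined protocol and SAP*

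**What the plan says.** Section 5.2 defines the primary outcome as "Proportion of patients prescribed an antibiotic in each arm by day 28". The GP records the day-0 decision at inclusion. For later prescriptions, section 8.5 (active surveillance) has the study team "record additional antibiotic prescription" in the calls at days 7 and 28, and section 9.3 lists the item for both calls.

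On patients who cannot be contacted, section 7.2 states: "Patients who are not reachable during follow-up will not have outcome data". It takes them out of the safety analysis, but for prescribing "they will still be included in the assessment of impact on antibiotic treatment and of the feasibility of the intervention". Section 11.4 agrees on inclusion: "The primary analysis will include all patients enrolled in the study, irrespective of follow-up". It then sets a rule for lost patients: "Patients who are lost to follow-up will be considered as having had a clinical failure, an adverse outcome and duration of disease", the last of these set to the longest duration seen in the others. Antibiotic prescription is not on that list. Section 11.5 expects some loss and adds no rule for it. (Sections 7.2 and 11.4 also disagree on the safety outcomes of these patients; that is a separate matter.)

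Three other provisions bear on the point:

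- Section 8.5 (passive surveillance) covers follow-up visits planned by the GP and returns for deterioration, with a short eCRF that includes the antibiotic decision.
- For patients who decline the phone interview, section 7.2 says that "the investigators can access the medical file until the end of the 28 days observation period". When a GP leaves the study, file access is settled case by case.
- Section 3.4 says that on worsening "patients will be advised to consult their GPs or an emergency care centre". Section 9.2 lets patients change GP, and defines loss to follow-up by the telephone interviews not being feasible.

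**The concern.** The primary analysis needs a day-28 value for patients who, by the plan's own statement, have none. Unless a return to the study GP was recorded, the only antibiotic information left is the day-0 decision, and a day-28 outcome becomes a day-0 outcome for that group.

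Only patients without a day-0 antibiotic can be misclassified. The interventions work by withholding antibiotics at day 0, and section 3.4 counts later prescription on worsening as one of the safety layers. If those later prescriptions are missed more often in the intervention arms, the estimated reduction is too large. That matters because section 11.1 treats a reduction below 15 points as too small to justify wider use.

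**Working it through.** **Sources of antibiotic information after day 0, for a patient reached by neither call**

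| Route | Covers this patient? |
|---|---|
| Day-7 and day-28 calls (8.5, 9.3) | No |
| GP eCRF at a planned or unplanned return (8.5) | Only if the patient goes back to the study GP |
| Symptom diary (8.5) | The six listed items are symptoms and activity, not antibiotics |
| Medical file (7.2) | Stated for phone refusers and, case by case, when a GP discontinues; not stated for the unreachable |
| Emergency centre or another GP (3.4, 9.2) | No source stated |

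**Inputs**

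- p28: 60% usual care, 45% PCT, 30% UltraPro (section 11.2). These are read as day-28 proportions, because 5.2 and 11.1 define the outcome by day 28.
- L, the share unreachable: not given; assumed 5% to 20%.
- r, later prescribing among patients untreated on day 0: not given; assumed 5% to 20% and equal across arms, or 5/15/25% (usual care/PCT/UltraPro).
- c, the share of unreachable patients' later prescriptions still captured by the GP eCRF: not given; set to 0 unless stated.

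**Formulas**

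- Day-0 proportion: p0 = (p28 − r)/(1 − r)
- Share whose only antibiotic comes later: g = (1 − p0) × r = r × (1 − p28)/(1 − r)
- Missed share: m = L × g × (1 − c); observed proportion = p28 − m
- Bias in a gap between two arms = m in the arm with fewer prescriptions − m in the other

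With L = 0 the model returns 60/45/30% and the planned gaps of 15, 15 and 30 points. The plan has no figure of its own for this bias.

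**Example, L = r = 10%**

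- Usual care: g = 0.10 × 0.40/0.90 = 4.44%; missed 0.44 points
- PCT: g = 0.10 × 0.55/0.90 = 6.11%; missed 0.61 points
- UltraPro: g = 0.10 × 0.70/0.90 = 7.78%; missed 0.78 points

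A true 15-point gap is observed as 15.17, and 30 as 30.33.

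**Unequal r of 5/15/25%**

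g = 0.05 × 0.40/0.95 = 2.11%; 0.15 × 0.55/0.85 = 9.71%; 0.25 × 0.70/0.75 = 23.33%. At L = 20%, usual care versus UltraPro: 0.20 × (23.33 − 2.11) = 4.25 points, from unrounded g.

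**Points added to each gap (c = 0)**

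| L | r | Usual care v PCT | PCT v UltraPro | Usual care v UltraPro |
|---|---|---|---|---|
| 5% | 5% all arms | 0.04 | 0.04 | 0.08 |
| 10% | 10% all arms | 0.17 | 0.17 | 0.33 |
| 20% | 20% all arms | 0.75 | 0.75 | 1.50 |
| 10% | 5/15/25% | 0.76 | 1.36 | 2.12 |
| 20% | 5/15/25% | 1.52 | 2.73 | 4.25 |

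With c = 0.5 every entry halves.

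**When the direction changes**

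- Equal loss of 20% and later-only shares of 6/4/4%: 0.20 × (4 − 6) = −0.4 points for usual care versus either intervention.
- r = 10% in all arms, but loss of 20% in usual care and 5% in UltraPro: 0.05 × 7.78 − 0.20 × 4.44 = 0.39 − 0.89 = −0.50 points.

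**Opposite convention**

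If every unreachable patient untreated on day 0 is counted as prescribed, the observed proportion is p28 + L × (1 − p28). A 15-point gap becomes 15 × (1 − L): 14.25, 13.5 and 12.0 points at L = 5, 10 and 20%.

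**The case against.** The strongest reply is that nothing in the plan codes these patients as having had no antibiotic. That is correct. A reader might infer such a rule, but the text is silent; the coding is only the likely result of keeping everyone in with no value and no rule.

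A reader might also infer that the bias must favour the interventions. The documents give no loss rate or later-prescribing rate by arm, and the working shows conditions under which the bias is zero or reversed. Nor does the design state that 70%, 55% and 40% of patients leave day 0 untreated: these are complements of proportions planned for day 28.

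Other points stand in part:

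- **Visits to the study GP.** Section 8.5 captures prescriptions at planned and unplanned returns and steers deteriorating patients back to the same GP. A patient reached on day 7 but not day 28 also has early prescriptions recorded. Both shrink the bias; neither covers care elsewhere.
- **Medical files.** A reader might conclude that file access is closed for the unreachable. It is unstated, not excluded: section 2.7 tells all participants that their records may be examined, and section 2.8 allows access for data verification. The case report, diary and consent forms are not in the documents, so what they collect or permit cannot be judged.
- **Per-protocol analysis.** Section 11.4 drops patients without complete telephone follow-up from it, which removes this group. It also drops patients whose GP did not follow the algorithm, so a difference from the primary result could not be attributed to missing follow-up.
- **Materiality.** With a design effect of 1 + 14 × 0.06 = 1.84, the effective size is 210/1.84 = 114.1 per arm, and the standard error for usual care versus UltraPro is √((0.60 × 0.40 + 0.30 × 0.70)/114.1), about 6.3 points. The equal-rate biases are small beside that. The larger figures need unequal later prescribing, for which the documents offer no number.

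**Conclusion.** The point holds as a gap in the handling of the primary outcome. Sections 7.2 and 11.4 require a day-28 antibiotic status for patients whom 7.2 describes as having no outcome data, and no section says how to obtain or assign it. For those without a recorded return to the study GP, the outcome would in practice rest on the day-0 decision.

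The direction is conditional. It favours the interventions if loss is similar across arms and later prescribing among untreated patients is similar or higher in the withholding arms. The size rests on assumed rates: less than one point per adjacent comparison when loss and later prescribing are equal across arms and no more than 20%, and about 2.1 to 4.25 points for usual care versus UltraPro under the 5/15/25% scenario at 10% to 20% loss.

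This would not overturn a clear result. It could matter near the 15-point threshold: a true adjacent gap of 15 points reads as 15.17 under one unstated convention (10% loss, 10% later prescribing) and 13.5 under the other (10% loss). The sponsor should settle the rule before the data are seen.

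**What to change.** 1. In sections 7.2 and 9.2, extend the medical-file check already foreseen for phone refusers to every patient, in any arm, without a completed day-28 interview, except those who withdrew from the study. The study team would look for antibiotics prescribed up to day 28, including any shown in emergency or discharge letters held by the study GP.
2. In section 11.4, state that where no call, GP eCRF or file covers the period to day 28 and no antibiotic is recorded, the primary outcome is missing. Impute it by arm, allowing for GP.
3. Add one sensitivity analysis that counts these patients as prescribed.

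The cost is some protocol wording, and consent wording if the current form does not already cover this access; a few file queries; one extra analysis; and slightly wider intervals. Patient management is unchanged.
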